#### 6.1.4.1. Multiple Imputation

The multiple imputation (MI) procedures for the primary and key secondary endpoints are described below.

For the primary analysis, missing data not due to mortality, and not addressed by the averaging rules above, will be imputed using the following regression-based multiple imputation model.

The following imputation algorithm will be applied to each SSS subscore separately, then the primary outcome SSS score will be derived.

1. The first step is to understand the pattern of missingness. In order to perform the multiple imputation, a monotone missing pattern must be achieved. For example, if there exist values for baseline and Day 2 visits, but missing values for the Day 1 (8-10h) visit, Markov-Chain Monte-Carlo (MCMC) method will be used to impute the small amount of missing data that may be missing at the intermediate visits that is required to make the missing data pattern monotone before applying the multiple imputation algorithm. This method uses a non-informative Jeffreys prior to derive the posterior mode from the expectation-maximization (EM) algorithm as the starting values for the MCMC method. This MCMC method will use seed of 432832. To avoid values that could not be observed in practice, imputed values will be constrained to be integers in the range of 0 to 3 or 0 to 4 by convention to align with the scale of the questionnaire. A total of 10 imputations will be done in the MCMC step.
2. Once the monotone pattern is achieved, the next step is to implement the imputation algorithm. For this, the Predictive Mean Matching method (PMM) will be used. This method is particularly helpful if the normality assumption is violated. For subjects with complete data up to a particular visit, a PMM model will be fit that includes the outcome at that visit as the dependent variable; and as independent variables gender, treatment assignment, study site, and non-missing scores using a seed of 931428. This process will be repeated 15 times, resulting in a total of 150 complete analysis datasets.
3. For each completed dataset, any necessary derived variables will be computed. Then the ANCOVA model will be performed for the 6 and 9 hour average SSS score. The results will be combined into one MI inference (LS mean, associated 95% CI, and p-value) using PROC MIANALZE as illustrated (Ratitch et al., 2013).

The first key secondary analysis on AUC will use the same process above, except in step 3 the AUC will be derived for each subject in each imputed dataset, then analyzed and aggregated as above using PROC MIANALZE (Ratitch et al., 2013).

The secondary key secondary analysis on antivenom amounts will not use multiple imputation.

The third key secondary analysis on NPRS AUC will use the same process above, except in step 3 the NPRS-AUC will be derived for each subject in each imputed dataset, then analyzed and aggregated as above using PROC MIANALZE (Ratitch et al., 2013).

The fourth key secondary analysis on CGI-I will use the same MI method described above, except using baseline and post-baseline CGI-I scores.

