#### **6.1.4.2. SAS Code for Multiple Imputation**

See below for SAS code describing the multiple imputation approach.

Step 1:

```
proc mi data=&base._tr out=&base._mcmc seed=432832 nimpute=10
minimum=0 maximum=&maxval. round=1;
  mcmc impute=monotone prior=jeffreys;
  em maxiter = 300;
  var visit1-visitN;
run;
```

Step 2:

```
proc mi data=&base._mcmc seed=931428 nimpute=15 out=&base._pmm
minimum=0 maximum=&maxval. round=1;
  by _imputation1_;
  class sexn trt01pn countryn;
  monotone regpmm(visit1-visitN) ;
  var sexn age trt01pn countryn visit1-visitN;
run;
```

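### Bounding and rounding the MCMC draws in the first imputation step biases intermittently missing SSS subscores, upward if most are 0; SSS-AUC is more exposed than the primary endpoint

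*SAP*

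**What the plan says.** SAP 6.1.4.1 imputes each SSS subscore in two steps. Step 1 makes the missing pattern monotone by filling, with MCMC, "the small amount of missing data that may be missing at the intermediate visits". There, "imputed values will be constrained to be integers in the range of 0 to 3 or 0 to 4". The code in SAP 6.1.4.2 uses "mcmc impute=monotone prior=jeffreys" with "minimum=0 maximum=&maxval. round=1", and its variable list is only "var visit1-visitN".

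Step 2 uses predictive mean matching, for this reason: "This method is particularly helpful if the normality assumption is violated". No such remark is made about step 1.

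Other rules come first (SAP 6.1.4). For the primary endpoint, if one of the 6 h and 9 h scores is missing, the other is used alone. If both are missing, the blinded site investigator scores them from contemporaneous records. Only what is still missing is imputed. SSS-AUC has the investigator step but not the single-score rule.

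The primary endpoint has a tipping point analysis (SAP 6.1.4.3). The key secondary endpoints get a missing-data sensitivity analysis only if more than 10 results cannot be calculated, and its form is left to data review.

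**The concern.** A normal model fitted to scores that are mostly 0 places much of its mass below 0. Bounding at 0 and rounding removes that lower tail but keeps the upper one, so the imputed values average too high. The SAP guards against non-normality only in step 2, when intermittent gaps are already filled.

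Step 1 is also probably the main route for any primary value that does get imputed. A patient missing both 6 h and 9 h but seen on Day 2 has a non-monotone pattern, and the SAP's own example (baseline and Day 2 present, 8-10 h missing) is of this kind.

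At stake are the imputed composite scores, any treatment difference if gaps are more common in one arm, and SSS-AUC, where one late visit carries a large time weight.

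**Working it through.** **1. The plan's own figures.** For a difference of 1.1, SD 1.75, two-sided 0.05 and 85% power (SAP 3.2), the normal formula gives 46 per arm. The t-test gives power 0.847 at 46 and 0.854 at 47 per arm, so 94 is reproduced. 10 x 15 = 150 imputed datasets also agrees.

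**2. Mechanism, one subscore.** Assume 90, 6, 3 and 1% at scores 0 to 3. The mean is 0.06 + 0.06 + 0.03 = 0.15 and the SD is √(0.27 − 0.15²) = 0.497. A normal with these moments has probability 0.381 below 0, 0.759 below 0.5, 0.997 below 1.5 and 0.905 above −0.5. The SAP does not say how out-of-range draws are handled, so three ways were tried:

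- Clip to the bounds: (0.997 − 0.759) + 2 × 0.003 = 0.244.
- Round, then redraw if out of range: 0.244/0.905 = 0.270.
- Redraw if out of range, then round: 0.244/0.619 = 0.395.

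All three exceed 0.15. By the same method, 80% zeros moves 0.30 to 0.42-0.63. A flat 0-3 scale stays at 1.50. A top-heavy hematologic subscore falls from 2.80 to 2.43-2.68.

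**3. Step 1 as coded.** The simulation used 94 patients, 7 visits, five subscores and a multivariate normal model with Jeffreys prior on the visits only (the model inferred from the code), with 150 replicates of 10 draws. Score distributions, visit correlations and missing rates are assumed. The 6 h and 9 h visits were missing. Bias in the primary change (baseline minus the 6 h/9 h average), in points per imputed patient:

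| Assumed set | Zeros at missing visits | Unbounded draws | Bounded and rounded |
|---|---|---|---|
| Correlation 0.8, 5-15% missing | 62-97% | +0.03 to +0.05 | −0.26 to −0.81 |
| Same, no treatment effect, 10% missing | 53-95% | +0.02 | −0.30 to −0.87 |
| Correlation 0.95, 10% missing | 66-97% | +0.02 | −0.11 to −0.33 |
| Less zero-heavy, 10% missing | 23-75% | +0.03 | −0.33 to −0.97 |

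A negative value means too little improvement. The unbounded draws are nearly unbiased, so the constraint is the cause. In a separate simulation with a true mean composite of 1.80, the bounded draws gave 2.34 to 2.88 (+0.54 to +1.08) and predictive mean matching gave 1.80.

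**4. Treatment difference.** With 10% balanced missingness it was 0.925 with unbounded draws and 0.917-0.925 with the constraint, a change of at most 0.008. In the less zero-heavy set it went from 1.856 to 1.830-1.846, a change of at most 0.026. If missingness differs by 10 percentage points between arms, the first row of the table gives 0.10 × 0.26 = 0.03 to 0.10 × 0.81 = 0.08. The design standard error is 1.75 × √(2/47) = 0.36, so that is about 8 to 22% of one standard error.

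**5. SSS-AUC weights.** Under the trapezoid in SAP 6.1.7.2, with Day 7 set at 168 h, the Day 3 score has weight (168 − t_Day2)/2. Day 2 falls 12-18 h after the 8-10 h visit, so t_Day2 is 20-28 h. The weight is (168 − 28)/2 = 70 to (168 − 20)/2 = 74 h, or 42-44% of the period. In the simulation (local wound left out), SSS-AUC was too high by 1-10 score-hours per imputed patient with 6 h and 9 h missing in the zero-heavy sets. With Day 2 and Day 3 missing it was too high by 15-46, against a mean of 136 (11-34%). Unbounded draws gave −2.8 in that case.

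**The case against.** The strongest objection is about reach. For the primary endpoint, step 1 is a third fallback after the single-score rule and blinded investigator scoring, and the SAP expects few such gaps. The tipping point analysis then tries all values toward the null, whatever step 1 produced. This stands. A reader might infer that the primary result is materially biased, but the documents do not support that: nothing in them suggests unequal missingness between arms, and with balanced gaps the shift is 0.01-0.03 points.

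The direction is not certain either. The documents give no subscore distribution. Mostly-zero scores are plausible: patients can qualify on local wound alone, which is outside the primary composite; known renal impairment is excluded; and SAP 8.2.2 reports unexpectedly few severely neurotoxic patients. But Protocol Appendix A scores severe coagulation abnormality as 4 for enrolment, so a top-heavy hematologic subscore, biased downward, is also plausible.

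A reader might also infer that fully recovered patients are credited with organ dysfunction purely because of the bounds. That goes too far. Any random imputation gives positive scores to some patients whose true score is 0, and roughly a third to a half of that average excess would remain under predictive mean matching.

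Finally, the constraint is not step 1's largest defect. Its model omits treatment, although SAP 6.1.4 bases the imputation on it. In the simulation with 10% missing, draws without treatment in the model lowered the difference from 0.996 to 0.925 before any bounding. This stands and belongs in the fix.

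**Conclusion.** The point holds as a minor, inexpensive improvement. Bounded and rounded normal draws bias the values filled in step 1: upward by roughly 0.1 to 0.9 composite points per patient imputed at 6 h and 9 h if subscores are mostly 0 (up to 1.08 in other assumed sets), and downward for a top-heavy subscore. The sizes rest on assumed distributions, visit correlations and missing rates, and on an inferred normal model with unspecified handling of the bounds.

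For the primary endpoint the consequence is small: 0.01-0.03 points with balanced missingness and about 0.03-0.08 with a 10-point imbalance, against 1.1.

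SSS-AUC deserves more attention. It is the first key secondary endpoint in the fixed testing sequence, has no single-score rule and weights Day 3 heavily. Its sensitivity analysis depends on results that cannot be calculated, and since imputation makes results calculable, that condition may never be met. The documents give no SD or target difference for SSS-AUC, so its bias cannot be set against a design value.

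**What to change.** Fill intermittent gaps with predictive mean matching (for example PROC MI with FCS REGPMM over the visits) or an ordinal model. Include treatment, country, sex and age, as SAP 6.1.4 states; the step 2 code already lists them. Drop `minimum=`, `maximum=` and `round=`: predictive mean matching returns observed scores, so they are not needed.

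The cost is a few lines of SAS and a revised description of step 1, made before unblinding. If one FCS call replaces both steps, the 10 x 15 description must be restated as well. The statistical downside is small: rare high scores have few donors.

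If the sponsor prefers to keep step 1, this method should at least be pre-specified as an unconditional sensitivity analysis for SSS-AUC.

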10.3.1.1 Composite Snakebite Severity Scale

The SSS (Dart RC et al., 1996) is a tool that was developed to measure the severity of envenoming based on 6 body system categories. The composite SSS score to be used, herein, is based on 7 categories and includes respiratory paralysis, acute renal failure, major thrombotic events, and death.

The renal system category will be used to characterize the severity of acute renal injury (scoring provided in appendix B). The baseline value for serum creatinine will be defined as the most recent serum creatinine in the past year, if one is available, or as the normal expected value for the patient.

Severe weakness or paralysis, including respiratory paralysis, will be scored a 3 in the nervous system section. Major thrombotic events will be scored in the appropriate SSS category as clinically presented. Death will be scored as the maximum score in each section.

The seven body systems are included as follows:

- Local wound (e.g., pain, swelling and ecchymosis)
- Pulmonary
- Cardiovascular
- Gastrointestinal
- Hematologic
- Nervous system
- Renal

OPX-PR-01

Each of these 7 categories are graded at levels from Grade 0 to Grade 3 (pulmonary, cardiovascular, gastrointestinal, nervous, and renal systems) or Grade 0 to Grade 4 (local wound and hematologic symptoms). A higher score indicates worse signs or symptoms. SSS scores will be performed by study personnel using the scoring sheet provided in Appendix B. At each assessment timepoint, each of the 7 SSS subscores should be recorded and a justification for each score should be provided.

10.3.1.2 Clinical Global Impression-Improvement

The CGI-I provides a clinician-based overall rating of the patient's condition (i.e., severity, distress, impairment and impact on functioning) in comparison to previous clinical status. The CGI-I should be determined using all available information, such as interviews with patients and family members, reports from other providers (including prehospital and transfer reports), medical records, and prior laboratory data (Busner and Targum, 2007) (Appendix C1). Baseline rating should be in comparison to previous patient status. Additional CGI-I should be performed on Day 1 at 1, 2, and 3 hours post initial dose, then follow normal assessment schedule as provided in the Schedule of Events. All post-baseline CGI-I assessments should be compared to baseline CGI-I.

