The CGI-I is defined as a selection of one of the following at each assessment period:

- 1 = very much improved since the initiation of treatment
- 2 =much improved
- 3 = minimally improved
- 4 = no change from baseline (the initiation of treatment)
- 5 = minimally worse
- 6 = much worse
- 7 = very much worse since the initiation of treatment

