Appendix C1:Clinical Global Impression-Improvement (CGI-I) Form

Baseline CGI-I rating should be in comparison to previous clinical assessments. Additional CGI-I should be performed on Day 1 at 1, 2, and 3-4 hours post initial dose, then follow normal assessment schedule as provided in the Schedule of Events. All post-baseline CGI-I assessments should be compared to baseline CGI-I.

Patient Name:	Date:
Clinician Name:	
Clinical Glob	oal Impression – Global Improvement (CGI –I) Scale
Rate total in drug treatm	nprovement whether or not, in your clinical judgment, it is due entirely to ent.
Compared to his/h	ner condition at baseline, how much has he/she changed?
	0 = Not assessed
	1 = Very much improved
	2 = Much improved
	3 = Minimally improved
	4 = No change
	5 = Minimally worse
	6 = Much worse
П	7 = Very much worse

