### **8.1.2.4. Clinical Global Impression – Improvement (CGI-I) at Day 2**

CGI-I (1-7 scale) at Day 2 will be treated as a continuous variable with scores compared using ANCOVA, with treatment as the variable of interest, and with baseline SSS, age group, baseline CGI-I score, baseline neurotoxicity, and country as covariates. The model will be used to estimate the effect of treatment on CGI-I scores at Day 2. The comparison of varespladib-methyl to placebo (varespladib-methyl vs. placebo) will be tested at a 5% two-sided significance level;

the corresponding p-value and 95% two-sided confidence intervals will be presented.

A sensitivity analysis will add completion of initial dose of antivenom prior to initiation of study drug as a covariate. Subgroup analyses will estimate the treatment effect separately for pediatric and adult patients, for patients with and without clinically significant neurotoxicity, for patient who have and have not completed an initial dose of antivenom prior to randomization, for the U.S. and for India, for each snake type (viper, elapid, and unknown), and for patients for whom the time from bite or symptom onset to receipt of study drug was <5 hours and  $\geq 5$  hours.

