### **8.3.6. Clinical Global Impression – Improvement (CGI-I) from Baseline through Day 28**

Descriptive summaries of absolute value and change from baseline of CGI-I will be tabulated by treatment group and visit and depicted graphically.

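### The CGI-I imputation inherits a floor of 0 although valid ratings run from 1 to 7, and SAP 8.3.6 subtracts CGI-I ratings that have different reference points

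*SAP*

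**What the plan says.** Protocol 10.3.1.2 defines seven CGI-I grades. The lowest is "1 = very much improved since the initiation of treatment"; 4 means no change, and 5 to 7 are degrees of worsening. The form in Protocol Appendix C1 adds an eighth code that is not a rating: "0 = Not assessed".

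The reference point differs by visit. The baseline rating compares the patient with his or her earlier clinical status. After that, "All post-baseline CGI-I assessments should be compared to baseline CGI-I". Under Protocol 8.2.1, patients who have already completed an initial antivenom dose (Category 2) can enter only with a CGI-I of 5 or more.

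SAP 8.1.2.4 makes Day 2 CGI-I the fourth and last key secondary endpoint: "CGI-I (1-7 scale) at Day 2 will be treated as a continuous variable with scores compared using ANCOVA". The model code in SAP 8.1.3 takes the rating itself as the response, not a change.

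For missing ratings, SAP 6.1.4.1 states: "The fourth key secondary analysis on CGI-I will use the same MI method described above, except using baseline and post-baseline CGI-I scores". The method it points to is described for SSS subscores. It restricts imputed integers to 0–3 or 0–4, and the stated purpose is to keep out scores that no patient could receive. In SAP 6.1.4.2 both PROC MI calls carry "minimum=0 maximum=&maxval. round=1": the maximum is a macro variable, but the minimum is a literal. No range is given for CGI-I.

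For the exploratory CGI-I analysis, SAP 8.3.6 states: "Descriptive summaries of absolute value and change from baseline of CGI-I will be tabulated by treatment group and visit". SAP 8.3.7 plans the same for PGIC.

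**The concern.** A plan that is followed as written should not generate values off the scale. Here it can. A CGI-I of 0 is one step better than the best possible rating, and it would enter an alpha-protected comparison that treats the score as continuous. The plan's own checks are unlikely to reveal it. The tipping-point analysis covers only the primary endpoint. A missing-data sensitivity analysis for the key secondaries is triggered only if results cannot be calculated for more than 10 participants (SAP 6.1.4).

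The subtraction in SAP 8.3.6 is a separate defect. A post-baseline CGI-I is already a statement of change since baseline. Taking away a baseline rating that describes change from some earlier state gives a number with no clear meaning, and its sign can contradict the clinician's rating.

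**Working it through.** **Inputs.** From the documents: valid range 1–7; code minimum 0; text range 0–3 or 0–4; Category 2 baseline 5–7; 94 evaluable patients randomised 1:1, so 94/2 = 47 per arm. The documents state no figure for CGI-I that could be reproduced, and they give no CGI-I mean, SD or missing-data rate. Those are assumed below and varied.

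**Step 1: where a 0 can arise.** The MCMC step fills intermittent gaps, such as Day 2 missing with Day 3 present, by drawing from a normal model, rounding to an integer and keeping the draw within bounds. With a floor of 0 it can return 0. The second step, predictive mean matching, copies values from donors. It cannot create a 0, but it treats first-step values as data and so can pass one on.

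**Step 2: how often, and by how much.** For a predicted rating with mean μ and SD σ, limited to 0–7:

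P(0) = [Φ((0.5−μ)/σ) − Φ((−0.5−μ)/σ)] / [Φ((7.5−μ)/σ) − Φ((−0.5−μ)/σ)]

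The mean imputed rating with a floor of 0 is compared with the mean from the same draw with a floor of 1.

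| μ | σ | P(0) | mean, floor 0 | mean, floor 1 | shift |
|---|---|---|---|---|---|
| 1.5 | 0.7 | 7.5% | 1.505 | 1.627 | 0.121 |
| 1.5 | 1.3 | 16.9% | 1.678 | 2.020 | 0.342 |
| 2 | 1 | 6.1% | 2.019 | 2.150 | 0.131 |
| 2.5 | 1 | 2.1% | 2.505 | 2.560 | 0.055 |
| 3 | 0.7 | <0.1% | 3.000 | 3.001 | 0.001 |

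Across μ of 1.5–3 and σ of 0.7–1.3, the share of zeros runs from below 0.1% to 16.9%. The imputed mean is 0.001 to 0.342 points too favourable.

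**Step 3: effect on an arm mean.** Multiply the shift by the share of the arm imputed in the MCMC step, assumed to be 5–10%:

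- Central case: 0.131 × 0.05 = 0.007 and 0.131 × 0.10 = 0.013.
- Extreme case: 0.342 × 0.05 = 0.017 and 0.342 × 0.10 = 0.034.

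The bounds are the same in both arms. The shift grows as the predicted rating nears 1, so it moves the better-faring arm slightly more, whichever arm that is.

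**Step 4: the text range read literally.** With a cap of 4 as well, at μ = 3 and σ = 1.3 the imputed mean is 2.696, against 3.013 for 0–7. That is 3.013 − 2.696 = 0.317 points too favourable, because imputed ratings of 5 to 7 are ruled out.

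**Step 5: the subtraction in SAP 8.3.6.**

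- A rating of 4 (no change) after a Category 2 baseline of 5, 6 or 7 gives 4−5 = −1, 4−6 = −2 or 4−7 = −3, an apparent improvement.
- A rating of 5 (slightly worse) after a baseline of 6 or 7 gives −1 or −2, also an apparent improvement.
- A rating of 4 after a baseline of 1, 2 or 3 gives +3, +2 or +1, an apparent worsening.

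Category 2 patients all enter at 5 or more, so every one of them later rated unchanged is tabulated as improved.

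**Step 6: a recorded 0, only if it were analysed as a number.** One such value whose true rating is 2 would lower a 47-patient arm mean by 2/47 = 0.043. Five would lower it by 10/47 = 0.213.

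**The case against.** The strongest reply is that the intended range is obvious. The SAP calls CGI-I a 1–7 scale, gives its reason for bounding imputed values as staying on the questionnaire's scale, and supplies the code as a macro template. The 0–3 and 0–4 limits belong to SSS subscores. A careful programmer would use 1–7. The MCMC step is also meant for a small amount of data, and CGI-I is tested only if the primary and three earlier key secondary tests all succeed. This holds as to intent and size. It does not remove the gap: neither text nor code gives a CGI-I range, and only the maximum is left open to adaptation.

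Three stronger readings are tempting and are not supported.

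- **The error always favours varespladib.** A false 0 flatters whichever arm it falls in, and the bounds are common to both arms. Nothing in the documents ties it to treatment.
- **Assessments marked as not done enter the ANCOVA as the best score.** Code 0 appears on the form, but the documents do not say how it is stored or handled. The SAP's responder split in 8.2.13 (1–2 against 3–7) leaves no place for it. The most that can be said is that a set-to-missing rule is not written down.
- **The mismatched subtraction affects the gatekept test.** It does not. The Day 2 model analyses the rating itself, and the subtraction is confined to exploratory descriptive tables, where the absolute values are shown alongside.

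**Conclusion.** The point holds with limited reach. Applied as written, the plan can impute CGI-I ratings that do not exist, and this touches the fourth key secondary test. The effect is probably small: about 0.01 points on an arm mean in the central case and about 0.03 at the extreme of the range examined. This rests on assumed predicted ratings of 1.5–3, SDs of 0.7–1.3 and 5–10% of ratings filled by the MCMC step. The true size depends on the amount of missing Day 2 data, which the documents do not give. There is no basis for expecting it to favour the drug systematically.

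The change-from-baseline tables are wrong in a different way. They can show improvement of 1 to 3 points in patients rated unchanged, or worsening of 1 to 3 points where the baseline rating was 1 to 3. That misdescribes within-arm change in exploratory output and affects no planned test.

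**What to change.** - In SAP 6.1.4.2, use `minimum=1 maximum=7` for CGI-I in both PROC MI steps, and state that range in 6.1.4.1.
- In SAP 8.3.6, drop the change-from-baseline summaries for CGI-I and tabulate the ratings themselves. Do the same for PGIC in 8.3.7, which Protocol Appendix C2 also defines as a change rating.
- As a safeguard, state that form code 0 is set to missing before imputation and analysis.

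The cost is one changed code argument, two sentences of text and some deleted table columns. Sample size and data collection are unaffected. The changes should be made before unblinding.
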